### 6.5 All Time Points

If patient non-compliance with electronic surveys is identified, the study coordinator will attempt to contact non-compliant patient to either encourage him/her to either complete the surveys, or to directly obtain respective data points from them. Further, patients who are given diaries will receive daily reminder phone calls from the study coordinator in the 72 hours following discharge.

Complications will be recorded. These include cardiac arrest, acute respiratory failure, venous thromboembolism event, ileus, SSI, deep infections, urinary tract infection, nerve injury, pneumothorax.

Schedule of Events				
Study Activity	Pre-op Visit	Surgical Stay	Time from discharge to first post-op visit	Post-op Visit
Study Agent Administration		X		
Informed consent	X			
Randomization		X a		
Demographics	X			
History / Physical Exam	X			
Concurrent Meds	X			
Pain Scores	X	X	X	X
PROMs b	X			X
Satisfaction Scores c			X	X
Opioid Use		X	X	X
Adverse Event Evaluation		X	X	

a: In pre-op, will be performed by pharmacy  
 b: ASES, SANE, SST, VR-12 scores  
 c: Obtained at 72 hrs post-op and at 1st post-op visit

## 7 Statistical Plan

### 7.1 Sample Size Determination

Using an equal-variance t-test with a multiplicity-adjusted alpha of 0.0167 (0.05/3), we need 55 subjects per group in order to achieve 80% power to detect a true effect size of 0.66 or larger. The total sample size of 110 includes 10 additional patients to protect against an estimated attrition rate of 10%. The effect size was estimated using an established MCID of 2 for VAS pain scales and a standard deviation of 3.

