### 3.2 Number of Subjects

This study will require a sample size of 50 subjects per group in order to achieve 80% power. The target enrollment will be 110 total subjects in order to combat an expected attrition of 10%.

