#### Handling of Missing Data

Initial descriptive statistics will be performed to quantify univariate missingness and distribution of variables. Observed values that appear to be extreme will be verified with the research staff for accuracy. If extreme values do not appear to exhibit undue influence on the statistical methods they will be kept in the analysis. Otherwise they will be removed. Extreme values found to be erroneous will be corrected.

Missing values for outcomes (e.g. VAS, opioid consumption, etc) will be imputed using the last observation carried forward method. Since we expect downward trends in these observations as time from procedure increases, this method will provide a conservative between-treatment estimate of the effect (assuming the observations are missing at random and are roughly missing with equal frequency within each treatment group).

These results will be compared to the results of a linear mixed-model which doesn't require that every patient has data for every measure at every point in time. Instead, it all information recorded and only excludes those time points at which data is missing. For example, if a patient is missing data at 48 hours, then the linear mixed-model will only include the data at 24 hours and 72 hours. In contrast, the last observation carried forward method would use the observed value from 24 hours for the 48 hour value and then all three time points will be included. In both cases, the baseline values for VAS and opioid consumption must be known for the patient to be included in the analysis.

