#### Multiplicity

There is only one primary hypothesis so we will not adjust for multiplicity at the highest level. However, if the linear mixed-model shows that the time by treatment interaction term is statistically significant and we perform post-hoc pairwise comparisons, the Tukey-Kramer

method will be used to adjust for multiple comparisons. There are several secondary aims that we consider exploratory analyses and as such will not adjust for multiple comparisons.

**Primary Hypothesis:** The average post-op pain score, adjusted for baseline pain scores, over the 72 hours post-op will be significantly lower in the liposomal bupivacaine group.

The difference in post-operative numeric pain scores between the treatment groups over time will be analyzed using a linear mixed-model with an interaction term for time and treatment and will adjust for the baseline (pre-op) scores.

**Secondary Hypothesis 1:** The average post-op satisfaction score over the 72 hours post-op will be significantly lower in the liposomal bupivacaine group.

The difference in post-operative numeric satisfaction scores between the treatment groups over time will be analyzed using a linear mixed-model with an interaction term for time and treatment.

**Secondary Hypothesis 2:** Time to block cessation will be longer in the liposomal bupivacaine group than the standard bupivacaine group.

The difference in time to block cessation will be analyzed between treatment groups using a two sample t-test if necessary model assumptions are met or the Wilcoxon Rank-Sum test if assumptions are not met.

**Secondary Hypothesis 3:** Total opioid consumption will be significantly lower in the liposomal bupivacaine group.

The distribution of total opioid consumption for the two groups will be compared using a multiple linear regression model with a term to adjust for baseline opioid consumption.

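### Section 7.1 labels the enrolled number (55 per group) as the number needed for 80% power, where 50 is needed, and its alpha of 0.05/3 is tied to no test in section 7.2

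*Combined protocol and SAP*

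**What the plan says.** **Required number.** Section 7.1 plans on an equal-variance t-test and an effect size of 0.66 (a difference of 2 VAS points over an SD of 3). It states: "with a multiplicity-adjusted alpha of 0.0167 (0.05/3), we need 55 subjects per group in order to achieve 80% power". Its next sentence reads: "The total sample size of 110 includes 10 additional patients to protect against an estimated attrition rate of 10" per cent. Section 3.2 states: "This study will require a sample size of 50 subjects per group in order to achieve 80% power", with 110 to be enrolled to cover 10% attrition. Section 5.3 randomises 110 equally to two arms.

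**Alpha.** The only level attached to a test anywhere in the plan is 7.1's 0.0167. Under Multiplicity, section 7.2 says: "There is only one primary hypothesis so we will not adjust for multiplicity at the highest level". If the time-by-treatment interaction is "statistically significant and we perform post-hoc pairwise comparisons, the Tukey-Kramer" method applies. For the rest: "There are several secondary aims that we consider exploratory analyses and as such will not adjust for multiple comparisons". The primary analysis is a "linear mixed-model with an interaction term for time and treatment and will adjust for the baseline (pre-op) scores". Section 7.2 gives no numeric alpha, and neither section says whether tests are one- or two-sided.

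**The concern.** There are two separate problems.

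1. Sections 3.2 and 7.1 give different required numbers for the same 80% power. Section 7.1 also disagrees with itself: if 110 already contains the attrition allowance, 55 per group cannot also be the number needed before attrition.

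2. The sample size rests on an alpha described as adjusted for multiplicity, with a divisor of 3, but the analysis section defines no family of three tests. The reader cannot tell which threshold decides the primary hypothesis.

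The second problem matters more. The first can be put right from the text alone. The second leaves open how a primary p-value between 0.0167 and 0.05 would be reported, which should be settled before the data are seen.

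**Working it through.** **Inputs, all from section 7.1 unless noted**
- Test: equal-variance two-sample t-test, equal groups (1:1 from section 5.3)
- Alpha: 0.05/3 = 0.0167
- Effect size: d = 0.66 (2/3 = 0.667 before rounding down)
- Power: 80%
- Sidedness: not stated, so both are tried

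**Formula.** With n per group, the t statistic has 2n − 2 degrees of freedom and noncentrality d × √(n/2). Power is the probability that it passes the critical t value at the chosen alpha. The required n is the smallest whole number that gives at least 80%.

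**Trying to reproduce 55**

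| Alpha | Sides | d | n per group for 80% |
|---|---|---|---|
| 0.05/3 | two | 0.66 | 49.5, so 50 |
| 0.05/3 | two | 2/3 | 48.6, so 49 |
| 0.05/3 | one | 0.66 | 41.6, so 42 |
| 0.05/3 | one | 2/3 | 40.8, so 41 |
| 0.05 | two | 0.66 | 37.02, so 38 |

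None gives 55. Two-sided at 0.05/3 and d = 0.66, power is 79.5% with 49 per group, 80.4% with 50 and 84.6% with 55. For 55 per group to give exactly 80%, the two-sided alpha would have to be about 0.0103, which appears nowhere in the plan.

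**Reproducing 50.** The two-sided calculation gives exactly the figure in section 3.2. Section 7.1's second sentence leads to the same place: 110 − 10 = 100, and 100/2 = 50 per group. Then 50 × 1.1 = 55 enrolled per group, or 110 in total. The allowance is 10/110 = 9.1% of those enrolled, so about 10%.

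**Looking for the source of the 3.** Each candidate in section 7.2 was compared with the text.
- Primary hypothesis: there is one, unadjusted at the highest level.
- Secondary hypotheses: three are listed, but the secondary aims are declared exploratory and unadjusted.
- Post-hoc pairwise comparisons: made only after a significant interaction, and adjusted by Tukey-Kramer, not by dividing alpha by 3.
- Time points: the missing-data text uses 24, 48 and 72 hours as an example ("from 24 hours for the 48 hour value and then all three time points will be included"). This could be the origin of the 3, but the plan does not say so.

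**What the choice of alpha changes.** For the planning t-test with 50 per group and d = 0.66, power is 80.4% at two-sided 0.05/3 and 90.45% at two-sided 0.05 (assumed). The difference, 0.9045 − 0.8044 = 0.10, is the chance that the t-test p-value falls between the two thresholds when the planned effect is true. These figures describe the t-test and are not the power of the baseline-adjusted mixed model.

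**The case against.** **On 55 versus 50.** The slip corrects itself: 7.1's next sentence, section 3.2 and the randomisation of 110 all point to 50 evaluable and 55 enrolled per group. That stands, and taken alone this is an editorial correction. It also has to be granted that 50 depends on a two-sided test, which the plan never states, and the primary hypothesis is worded directionally. But the one-sided answer, 42, is further from 55, so the missing sidedness does not rescue the figure.

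A reader might infer that 55 evaluable per group really are needed and that 110 is therefore too few. The documents do not support this, because 7.1's own inputs give at most 50 and its total is stated to include the attrition allowance.

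**On the alpha.** Section 7.1 governs sizing and section 7.2 governs testing. A stricter alpha can be used for sizing, as conservative planning or as a Bonferroni stand-in for comparisons at three time points, while the primary test stays unadjusted. The phrase about the highest level leaves room for adjustment lower down, and the numerator in 0.05/3 suggests that the undivided level is 0.05. All of that is fair. A reader might infer that 7.1 and 7.2 flatly contradict each other. The text does not go that far, because the two can coexist. What remains is an omission: the plan does not give the conservative-planning explanation, name three tests or put a number on the primary threshold.

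**Conclusion.** Both parts hold, within limits.

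- **Required number.** The 55 in section 7.1 is wrong as a requirement for 80% power. The figure is 50, assuming a two-sided test, which section 3.2 and the attrition sentence support. The overstatement is 5 per group, or 84.6% power where 80% is claimed.
- **Alpha.** The 0.05/3 in section 7.1 has no stated counterpart in section 7.2, and the primary test has no numeric threshold. If two-sided 0.05 was intended, the planning t-test with 50 per group has about 90% power for d = 0.66. If 0.0167 was intended, section 7.2 lacks the rule.

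Both errors are conservative for power. A reader might infer that the trial is underpowered or should enrol more, but neither error supports that. The point should be fixed mainly because of the open threshold; the label is secondary.

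**What to change.** 1. In sections 3.2 and 7.1, write: 50 evaluable and 55 enrolled per group (110 in total, allowing for about 10% attrition).
2. State one numeric alpha and the sidedness for the primary test, identically in 7.1 and 7.2.
3. If that is an unadjusted two-sided 0.05 (an assumption here), replace 0.0167 in 7.1 and restate the planning power with 50 per group as about 90% for d = 0.66. Label it as t-test power, not that of the baseline-adjusted mixed model.
4. If 0.0167 is kept, name the three tests it covers, write the same rule into 7.2, and correct 55 to 50 per group for 80% power.

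The cost is wording in three sections. Enrolment stays at 110 either way, with no change to data collection. The change should be made before any unblinded analysis.

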### 7.2 Statistical Methods

#### Descriptive Statistics

Univariate descriptive statistics for categorical variables will include frequency and percent and for numerical variables will include mean, standard deviation, median, and range (minimum value, maximum value). Univariate tests of these variables with the treatment variable will be performed with either the Chi-Square test or two sample t-test in order to identify potential confounders.

#### Handling of Missing Data

Initial descriptive statistics will be performed to quantify univariate missingness and distribution of variables. Observed values that appear to be extreme will be verified with the research staff for accuracy. If extreme values do not appear to exhibit undue influence on the statistical methods they will be kept in the analysis. Otherwise they will be removed. Extreme values found to be erroneous will be corrected.

Missing values for outcomes (e.g. VAS, opioid consumption, etc) will be imputed using the last observation carried forward method. Since we expect downward trends in these observations as time from procedure increases, this method will provide a conservative between-treatment estimate of the effect (assuming the observations are missing at random and are roughly missing with equal frequency within each treatment group).

These results will be compared to the results of a linear mixed-model which doesn't require that every patient has data for every measure at every point in time. Instead, it all information recorded and only excludes those time points at which data is missing. For example, if a patient is missing data at 48 hours, then the linear mixed-model will only include the data at 24 hours and 72 hours. In contrast, the last observation carried forward method would use the observed value from 24 hours for the 48 hour value and then all three time points will be included. In both cases, the baseline values for VAS and opioid consumption must be known for the patient to be included in the analysis.

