### 1.3 Risks and Benefits

The most significant risks associated with this study are directly related to surgery itself.

Risks associated with the nerve block: Block failure, nerve injury, hematoma, infection, and pneumothorax

Serious risks associated with bupivacaine-containing products, while extremely rare, include:

1. *Central nervous system reactions*: persistent anesthesia and paresthesias, excitation and/or depression
2. *Cardiovascular reactions*: dysrhythmias, death
3. *Allergic reactions*: anaphylaxis, angioedema.

Patients who are at highest risk of these complications including patients with severe liver and respiratory disease will be excluded from this study.

Potential benefits from participation in the study include improved post-operative outcomes: diminished post-operative pain, and decreased opioid consumption.

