### 4.2 Exclusion Criteria

- Non-elective cases
- Infection, tumor, trauma
- Weight < 50 kg
- Patients with any contraindications to regional anesthesia including allergy or hypersensitivity to amide-type local anesthetics
- Patients with allergy to any component of medication regimen e.g. amide-type local anesthetics, oxycodone, hydromorphone, fentanyl
- Chronic pain patients with history of chronic opioid use (defined as 20 mg morphine equivalent / day for greater than 30 days pre-operatively)
- Concurrent painful physical condition that may require analgesic treatment that is not related to the shoulder surgery (chronic peripheral neuropathy, radiculopathy, or other neurologic disorder)
- Severe hepatic disease defined by clinical evidence of liver disease with abnormal liver function tests.
- Pregnancy

- Respiratory disease that contraindicates interscalene nerve block (elevated contralateral hemidiaphragm, contralateral pneumonectomy, or severe COPD with FEV1 < 50% predicted, and O2 dependence)

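### Extreme values that were checked and not found wrong are deleted for being influential, with no cutoff and no analysis that keeps them; opioid totals are most exposed

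*Combined protocol and SAP*

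**What the plan says.** The rule stands in section 7.2, under Handling of Missing Data, and has three parts:

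- **Checking:** "Observed values that appear to be extreme will be verified with the research staff for accuracy".
- **Keeping or removing**, depending on whether a value appears to have "undue influence on the statistical methods they will be kept in the analysis. Otherwise they will be removed".
- **Correcting:** "Extreme values found to be erroneous will be corrected".

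The same subsection then sets last observation carried forward (LOCF) for missing outcomes and adds one comparison: "These results will be compared to the results of a linear mixed-model".

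Under Multiplicity, Secondary Hypothesis 3 states that total opioid consumption "will be compared using a multiple linear regression model with a term to adjust for baseline opioid consumption". The plan describes its secondary outcomes as "several secondary aims that we consider exploratory analyses". No transformation or rank-based fallback is given for opioid totals, whereas time to block cessation has a Wilcoxon fallback. Section 7.3 defines which patients are analysed and says nothing about deleting individual values.

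**The concern.** Errors have their own route, so the ground for deletion is influence on the result, not error. A patient with a genuine, verified high opioid total can be dropped because that total matters to the estimate.

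Such totals are foreseeable. Section 1.3 lists "Risks associated with the nerve block: Block failure, nerve injury, hematoma, infection, and pneumothorax", and a patient whose block fails may need far more opioid. Less opioid use in the liposomal arm is itself a hypothesis of the trial, so high users belong to the treatment comparison. If they are more common in one arm, deleting them distorts the difference.

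Two people applying the rule in good faith could also delete different values, because neither extreme nor influential is defined. The LOCF against mixed-model comparison would not reveal this, since it addresses values that were never observed. The plan also does not say whether a removed value is then treated as missing and imputed.

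**Working it through.** **Inputs from the documents.** Section 3.2 gives 50 per group. This reproduces from section 7.1: effect size 0.66, alpha 0.0167 (taken as two-sided) and 80% power give 49 per group by the normal approximation and 50 by the t-test (power 80.5%). The SD for pain is 3 (section 7.1). Section 4.2 excludes "history of chronic opioid use (defined as 20 mg morphine equivalent / day for greater than 30 days pre-operatively", which trims part of the upper tail of opioid use.

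**Assumed inputs.** The documents give no opioid distribution, failure rate or cutoff.

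- Totals are lognormal with log-SD 0.8 and mean 46 mg without block failure.
- Baseline use is zero in 80% of patients and uniform on 0 to 20 mg/day in the rest; each mg adds 1 mg to the total.
- The analysis is linear regression on arm and baseline use.
- A value is removed only if it lies outside a pooled 1.5-IQR boxplot screen **and** exceeds the cutoff. For Cook's D, 4/n = 4/100 = 0.04.

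**Expected differences with all values kept** (failure at 4x use adds 3 times the failure rate to the mean):

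- Failures 10% against 2%, 4x use: 46 x (1.06 - 1.30) = -11.0 mg.
- The same at 2x use: 46 x (1.02 - 1.10) = -3.7 mg.
- No failures, 30% lower use: -46 x 0.30 = -13.8 mg.
- Failures 5% in both arms at 4x use, 30% lower use: -46 x 1.15 x 0.30 = -15.9 mg.

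**Simulated mean differences (mg), 4,000 to 5,000 trials per row:**

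| Scenario | All values | Studentised residual above 3 | Cook's D > 4/n | Cook's D > 0.5 | Cook's D > 1 |
|---|---|---|---|---|---|
| 10% vs 2% failures, 4x | -11.0 | -4.9 | -3.9 | -10.0 | -10.9 |
| Same, totals capped at 300 mg | -8.6 | -4.0 | -3.1 | -8.5 | -8.6 |
| Same, totals capped at 200 mg | -7.0 | -4.8 | -2.8 | -7.0 | -7.0 |
| 10% vs 2% failures, 2x | -3.7 | -2.2 | -1.9 | -3.5 | -3.7 |
| No failures, 30% lower use | -13.7 | -10.8 | -9.9 | -13.4 | -13.6 |
| 5% failures in both arms, 30% lower use | -16.0 | -11.9 | -11.0 | -15.1 | -15.8 |

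Repeat simulations of the first row gave -10.3 to -11.0 with all values, and -4.6 to -4.9 and -3.7 to -3.9 under the two strict cutoffs.

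**Shrinkage.** In the first row, the strict cutoffs lose 6.1/11.0 = 55% and 7.1/11.0 = 65%. With no failures they lose 2.9/13.7 = 21% and 3.8/13.7 = 28%.

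**Who is removed (first row, mean per 100 patients, control share in brackets).** Residual above 3: 2.4 (1.6). Cook's D > 4/n: 3.9 (2.5). Cook's D > 0.5: 0.19 (0.14). Cook's D > 1: 0.06 (0.04).

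**Dependence on the cutoff.** The p < 0.05 result differs between the four cutoffs in 13% of trials in the first row, 15% with the 200 mg cap, and 29% with no failures and 30% lower use.

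**False positives (both arms alike, 5% failures, 4x).** All values give 4.9%; the four cutoffs give 6.5%, 6.7%, 5.2% and 5.0%. In a further run, taking the most favourable of the five analyses raised the rate from 4.3% to 10.4%.

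**Primary pain.** For scores on 0 to 10 with assumed mean 5 and SD 3, the quartiles are 5 - 0.6745 x 3 = 2.98 and 7.02, so the IQR is about 4.05. The boxplot limits are 2.98 - 6.07 = -3.1 and 7.02 + 6.07 = 13.1, both off the scale. Simulation agrees (1,500 trials, three scores per patient, correlation 0.5): at most 0.03 of 300 scores are removed, the difference stays at -1.76, and false positives stay at 4.2%. The estimate moves only in a wholly assumed low-pain setting (mean 2, SD 1.5, failed blocks at mean 7, 10% vs 2%): -0.39 becomes -0.30 and -0.19 under the strict cutoffs and is unchanged under the lenient ones.

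**The case against.** The strongest objections go to size.

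- **The headline scenario is assumed.** Block failure is listed without a rate or a difference between arms. Both arms use the same ultrasound guidance and level of operator, and section 5.5 checks block success in all patients. Putting the whole effect in the failed blocks is close to a worst case for shrinkage. With equal failures and 30% lower use, the strict cutoffs lose 4.1/16.0 = 26% and 5.0/16.0 = 31%, and power rises from 35% to 44-45%. This stands. The estimate still moves, however, and the p < 0.05 result differs between cutoffs in 31% of those trials.
- **The headline scenario has little power.** All-values power is about 11%, and the shift is about half a standard error. This also stands.
- **Lenient cutoffs do almost nothing.** True for Cook's D above 0.5 or 1, but the plan commits to neither.
- **Opioid data are recorded daily.** Section 2 names two windows, section 6.3 collects daily use to 72 hours, and LOCF is applied to opioid consumption. If a daily value were removed and imputed, the patient would stay in the analysis. The simulation drops the patient instead, so this variant has not been sized. The plan does not say which applies.
- **Statisticians are blinded (section 5.6).** A fixed cutoff applied blind still removes more control values and shifts the estimate. Section 5.3 also says the statistician has seen the randomization list, so blinded removal is not assured.
- **The outcome is exploratory and the primary is unharmed at SD 3.** Both are accepted, and they limit the seriousness of the point.

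**Conclusion.** The concern holds. As written, the rule deletes values that were checked and not found wrong because they influence the result, with no stated threshold and no analysis to show what deletion did. That reading rests on the text alone.

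The size is conditional on assumed opioid distributions and cutoffs. Under strict cutoffs, about one fifth to two thirds of the opioid difference is lost across the scenarios; under lenient ones, at most about one tenth. In every scenario with a true difference, the bias is toward no difference. Significance can move either way, because deletion also shrinks the standard error. With any single fixed cutoff the rise in false positives is small (at most 6.7% against 4.9%). It becomes material only if the cutoff is chosen after results are seen.

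No harm is shown for the primary pain outcome at the plan's SD. This should be fixed, but it does not threaten the primary conclusion.

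**What to change.** In section 7.2, delete the sentence that removes influential values and state instead:

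1. Documented errors are corrected. A value shown to be wrong that cannot be recovered is set to missing and listed, and the missing-data rule then applies to it.
2. Every other value stays in the primary and secondary analyses.
3. Results without influential points are reported only as a labelled sensitivity analysis, with the diagnostic and cutoff fixed before unblinding and the removed values listed by arm.

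This takes one or two sentences and no change of model. The cost is wider intervals, mainly for opioid totals: in the uncapped 4x scenario the mean standard error is 12.8 mg with all values, against 8.1 mg after removing residuals above 3 and 7.3 mg with Cook's D > 4/n. The narrower intervals come from discarding real patients' data. If skewness is the worry, a transformation or a robust or rank-based method specified in advance would address it without deletion, though it would change the quantity being compared.

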## 2 Study Objectives

The primary outcome measure will be:

1. Mean difference in patient pain scores over the first 72 hours post-operatively between two groups

Secondary outcomes will include:

1. Total opioid consumption (as measured utilizing morphine intravenous equivalents) in first 72 hours and at 3 weeks
2. Patient perceived duration of block determined as the time patient perceives complete resolution of block
3. Patient satisfaction with pain control at 72 hours, 3 weeks post-operatively and patient reported outcome measures (SANE, SST, ASES, VR-12) at 3 weeks post-operatively

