### 6.3 Time from discharge to first post-operative visit

At discharge, pain scores will be measured utilizing electronically managed surveys that will be e-mailed to each patient on a twice daily basis (upon waking the AM and just prior to bedtime) after discharge for the first 72 hours following surgery. Finally, patient satisfaction scores (Likert scores) will be emailed to the subjects at 72 hours.

Total opioid consumption will similarly be measured based off of electronically managed surveys or a written diary on a daily basis following discharge for the first 72 hours. All values will be presented as morphine equivalents.

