### 6.4 First Post-operative Visit (3-weeks post-op)

During the first follow-up visit, total opioid consumption during their post-operative course will be measured, and pain scales and satisfaction scores will be obtained including ASES, SST, SANE, VR-12. Total opioid consumption will be quantified by the number of narcotic prescription pills remaining. Opioid consumption will be standardized to morphine equivalents. All diaries will be collected at this time.

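### Last observation carried forward is prescribed for opioid consumption, but a missing 3-week cumulative total can then only be filled with a value that leaves out later use

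*Combined protocol and SAP*

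**What the plan says.** The missing-data rule in section 7.2 (Handling of Missing Data) names opioid consumption and makes no exception for totals or for the 3-week value: "Missing values for outcomes (e.g. VAS, opioid consumption, etc) will be imputed using the last observation carried forward method". The reason given is: "Since we expect downward trends in these observations as time from procedure increases, this method will provide a conservative between-treatment estimate of the effect". A condition is attached: "assuming the observations are missing at random and are roughly missing with equal frequency within each treatment group". The worked example covers 24, 48 and 72 hours only. A linear mixed model is offered as a comparison.

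Section 2 defines the first secondary outcome as "Total opioid consumption (as measured utilizing morphine intravenous equivalents) in first 72 hours and at 3 weeks". Section 6.3 collects home use through "electronically managed surveys or a written diary on a daily basis following discharge for the first 72 hours". At the 3-week visit, section 6.4 says "total opioid consumption during their post-operative course will be measured", and gives the method: "Total opioid consumption will be quantified by the number of narcotic prescription pills remaining". Secondary Hypothesis 3 in section 7.2 has the total "compared using a multiple linear regression model with a term to adjust for baseline opioid consumption".

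**The concern.** Carrying a value forward can be argued for when the quantity is a level at a point in time, such as a pain score. A cumulative total is different. It can only stay flat or rise, so carrying it forward asserts that nothing was consumed after the last record. The declining trend on which section 7.2 relies may describe daily amounts, but it cannot describe a total.

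The 3-week total is the exposed value. It rests on one count at one visit, and the last scheduled opioid record before that visit is at 72 hours. A patient whose count is missing would enter the regression with a total that omits about 18 days of possible use. Arm means would be too low. If the arms differ in missing counts or in late use, the comparison would be distorted on an outcome that the Introduction and Background name among the trial's aims.

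**Working it through.** The plan gives no opioid consumption figures, so it has no number of its own to reproduce on this point. The only planning input is the expected attrition of 10% (sections 3.2 and 7.1), or 0.10 × 55 = 5.5 patients per arm. Treating all of it as missing 3-week totals is an assumption.

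1. **Identity.** Let T72 be the 72-hour total, L the use from day 4 to day 21, and T21 = T72 + L. Carrying the total forward sets T21 = T72, so L = 0. If one day's amount is carried instead, a single day stands in for the whole course. Neither value can exceed the true total.

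2. **One patient.** Let s = T72/T21, assumed to lie between 0.3 and 0.7. The shortfall is 1 − s, or 70% to 30%. For illustration, with T72 = 60 units the true total is 60/0.3 = 200 or 60/0.7 = 86, and 60 is entered.

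3. **Arm mean.** Scale the true mean to 100 and let m be the fraction missing, unrelated to use. The mean after carrying forward is 100(1 − m) + 100·m·s. At m = 0.10:
   - s = 0.3: 90 + 3 = 93
   - s = 0.5: 90 + 5 = 95
   - s = 0.7: 90 + 7 = 97

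   Arm means are 7%, 5% and 3% too low.

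4. **Arm difference.** For arms A and B the bias in A minus B is −(mA·LA − mB·LB).
   - Equal m and equal late use: the bias is zero.
   - Equal m, different late use: the bias is −m(LA − LB). At m = 0.10 a true late difference of 20 units counts as 18. If late use is lower with liposomal bupivacaine, the benefit shrinks. If it is higher, the omitted use would have offset the early saving, so the benefit is overstated. The claim that the method is conservative therefore does not follow, even under the plan's own condition.
   - Unequal m (assumed 15% against 5%), identical true use:
     - s = 0.3: 89.5 against 96.5, difference 7
     - s = 0.5: 92.5 against 97.5, difference 5
     - s = 0.7: 95.5 against 98.5, difference 3

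     The false difference of 3-7% favours the arm with more missing data.

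5. **Scale against noise.** With an assumed coefficient of variation of 0.5 to 1.0 and 55 per arm, the standard error of the difference is CV × √(2/55), or 9.5% to 19% of the mean. A bias of 3-7% is then between 3/19 = 0.16 and 7/9.5 = 0.73 standard errors.

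6. **Standard error.** Take mean 100, m = 0.10, s = 0.3, with 72-hour use proportional to 3-week use. The variance after carrying forward is 0.9σ² + 0.1 × 0.09σ² + 0.09 × 70².
   - σ = 40: 1440 + 14 + 441 = 1895, above the full-data 1600 and above the complete-case equivalent 1600/0.9 = 1778.
   - σ = 100: 9000 + 90 + 441 = 9531, below the full-data 10000.

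   The effect on the standard error can go either way.

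**The case against.** The plan never says that the 72-hour total replaces the 3-week total. Its rationale and its example suit per-interval values, and home use to 72 hours is collected daily. Carrying a daily amount forward and then summing is a plausible reading within 72 hours, and if use declines it would over-count, not under-count. This stands for the 72-hour total. It does not rescue the 3-week total: that is a single measurement, no daily values are scheduled after 72 hours, and so there are no later daily entries for the rule to fill.

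A reader might infer that the imputed totals are impossible values. They are not. Discharge opioids are taken as needed, and one discharge option in section 5.5 is acetaminophen alone, so some patients may use none after 72 hours. The carried-forward total is a lower bound, probably too low on average. A reader might also infer that the standard error is bound to be understated; step 6 shows otherwise.

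The mixed-model comparison might be thought a safeguard. The missing-data text mentions opioid consumption in connection with both approaches, but Secondary Hypothesis 3 specifies only a linear regression on the total. The two places are unreconciled. That does not show that no comparison is planned, but it does not amount to a specified check either.

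Coordinator contact and reminder calls (section 6.5) should reduce missing reports in the first days. They are directed at surveys and diaries, so they do less for a missed pill count. The size of the problem is also limited: the bias in the comparison is conditional, and section 7.2 treats the secondary aims as exploratory.

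**Conclusion.** The concern holds for the 3-week total. The rule as written covers opioid consumption, its rationale cannot apply to a total, and either way of applying it to a missing 3-week value gives a lower bound that is then analysed as observed. Within 72 hours, carrying daily amounts may be acceptable, but the plan should say that daily amounts and not totals are carried.

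The sizes in the working rest on an assumed 72-hour share of 30-70% and on missingness unrelated to use; the false difference also rests on an assumed 15% against 5% split. None of these comes from the documents. A reader might infer that the plan will produce a spurious opioid-sparing result. The documents do not support that: they give no reason to expect unequal missingness or different late use, and with neither the arm difference is unbiased. The primary pain analysis is not affected. This is worth correcting because the stated rule gives a wrong kind of value and the correction is cheap.

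**What to change.** In section 7.2:

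- Exclude cumulative opioid totals from last observation carried forward. If the method is kept within 72 hours, state that daily amounts are carried and then summed.
- For a missing 3-week total, multiply impute the use from day 4 to 3 weeks from arm, baseline use, and observed in-hospital and daily use, then add it to the observed 72-hour total. Discharge prescription could be added as a predictor if it is recorded; sections 6.2 to 6.5 do not list it.
- Report the observed-data analysis alongside, with the number of missing 3-week totals in each arm.
- State whether the mixed-model comparison is meant to cover opioid consumption, so that the missing-data text and Secondary Hypothesis 3 agree.

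The cost is a change of wording, slightly more analysis work on variables already scheduled for collection, and possibly slightly wider confidence intervals for the opioid comparison. It should be settled before outcome data are examined by arm, so that the handling of missing totals is not chosen after the fact.
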